#### **Initiation of Phase 2a Expansion Cohorts**

Upon completion of any Phase 1 Expansion Cohort, the SRC may elect to expand the cohort further, initiating a Phase 2a Dose Expansion and enrolling an additional nine patients if the dose level meets the following:

- Two or more patients have experienced an objective response per RECIST v1.1 (i.e., a PR or CR), of which at least one is a confirmed response.
- There are no additional safety concerns in the cohort of existing patients based upon the SRC's analysis of emerging safety data.

The total number of patients enrolled at any one dose level during all phases of the study will not exceed 25 patients.

Based upon the above criteria, the SRC may elect to explore multiple dose levels as Phase 2a Expansion Cohorts (either staggered or concurrently).

#### **Duration of Therapy**

Patients may continue to receive treatment until meeting criteria for discontinuation/withdrawal, e.g., adverse events, disease progression, etc. as outlined in Section 6.11.

#### **Re-initiation of Therapy for Patients in Long-Term Follow-Up**

Patients having discontinued treatment after achieving a confirmed CR may reinitiate study therapy at the time of confirmed disease progression if there is agreement between the Investigator and the Sponsor.

Patients will be required to meet eligibility criteria at the time of reinitiating study drug and will receive the same dose level of VK-2019 that they received prior to discontinuation. However, if higher dose levels of VK-2019 have been explored and deemed tolerable by the SRC, the Investigator and Sponsor may agree that the patient may reinitiate VK-2019 at a higher dose level. Patients reinitiating VK-2019 at a higher dose level will not be evaluable for a DLT.

Patients resuming therapy in this setting will do so at the next cycle after they completed therapy and will be followed as specified for all patients in the study. For example, patients that discontinued therapy after Cycle 14 will reinitiate therapy at the beginning of Cycle 15.

Patients that achieved a CR will not be eligible to reinitiate treatment if they:

- Discontinued study drug due to a treatment related adverse event(s), or
- Have completed one year of follow-up (from date of last dose of study drug) without evidence of disease progression.

Additional safety and efficacy summaries will be presented for patients that reinitiated study therapy under these conditions.

## Patient Withdrawal

Patients may withdraw from the trial at any time at their own request, or they may be withdrawn at any time at the discretion of the investigator or sponsor for safety, behavioral, or administrative reasons. Patients that withdraw from treatment should be encouraged to return for the end-of-treatment visit, complete all safety assessments, and enter long-term follow-up. If the patient withdraws from both treatment and follow-up, no further evaluations should be performed, and no additional data should be collected. The Sponsor may retain and continue to use any data collected before such withdrawal of consent.

The primary reason for withdrawal must be recorded in the subject's medical record and in the appropriate eCRF pages. If a subject is withdrawn for more than one reason, each reason should be documented in the source document and the most medically significant reason should be entered on the eCRF. For example, in order to best characterize the safety profile of VK-2019, patients that withdraw consent from treatment due to tolerability issues with VK-2019 should be captured in the eCRFs as having discontinued due to AE or toxicity instead of having withdrawn consent from treatment.

Patients will be discontinued from treatment and begin long-term follow-up in the case of:

- Disease progression or requirement for anticancer therapy not specified in the protocol.
- Inter-current illness, general, or specific changes in the patient's condition where, in the opinion of the Investigator, further treatment is not in the best interest of the patient.
- DLT or unmanageable AE related to therapy.
- Withdraw of consent from treatment.
- Significant protocol violation or non-compliance with protocol.
- Termination of the study by Sponsor. Note: Any patients still receiving investigational product at the time of study termination by the sponsor will be able to continue to receive VK-2019 if they are deriving clinical benefit and after agreement between the Investigator and sponsor. Such patients will continue to be monitored for SAEs as

described in Section 13. Drug Accountability information must still be collected until all patients have completed treatment.

Patients will be withdrawn from study (long-term follow-up) in the case of:

- Withdrawal of consent from follow-up.
- Patient lost to follow-up.
- Death.
- Termination of study by Sponsor.

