# 9 PATIENT MONITORING, TOXICITY MANAGEMENT, AND DOSE MODIFICATIONS

Each patient will be assessed for the development of any toxicity as outlined in Section 13. Dose adjustments will be made according to the system showing the greatest degree of toxicity. The table below outlines parameters for dose holds, dose reductions, resuming dosing, and study drug discontinuance for AEs assessed to be at least possibly related to VK-2019.

Adverse Event	Action with VK-2019 and Toxicity Management
All Grade 1 AEs	Continue VK-2019 at the same dose level. Manage with supportive therapy at the Investigator's judgment.
All Grade 2 AEs	Continue VK-2019 at the same dose level. Manage with supportive therapy at the Investigator's judgment.
All Grade $\geq$ 3 AEs (unless otherwise noted below)	Hold VK-2019 and administer supportive therapy as required in accordance with local practice/guidelines.
	If AE resolves to Grade $\leq 2$ within 21 days, VK-2019 may be restarted at the same dose (unless meeting criteria for a DLT) or a lower dose pending discussion between the investigator and Sponsor.
	If AE does not resolve to Grade $\leq 2$ after 21 days, permanently discontinue VK-2019 and observe the patient until the AE is resolved.
Grade ≥ 2 diarrhea	Manage with Loperamide (4mg at first onset, followed by 2mg every 2-4 hours (or with each loose bowel movement) until diarrhea free for 12 hours (maximum daily dose: 16 mg/24 hours). If loperamide is ineffective, consider adding Lomotil (5 mg, four times a day), or tincture of opium (15- 20 drops orally every 4 hours), or octreotide (150 to 300 mcg SQ twice daily). Modifications to this regimen can be made per local standard practice.
	Hold VK-2019 and manage as above until resolves to Grade $\leq 2$ .
Grade $\geq$ 3 diarrhea	If diarrhea resolves to Grade $\leq 2$ within 21 days, VK-2019 may be restarted at the same dose (unless meeting criteria for a DLT) or a lower dose pending discussion between the investigator and Sponsor.
	If diarrhea does not resolve to Grade $\leq 2$ after 21 days, permanently discontinue VK-2019 and observe the patient until the AE is resolved.

Adverse Event	Action with VK-2019 and Toxicity Management
Nausea/vomiting, all grades	Standard antiemetics for the treatment of nausea and/or vomiting may be used. If it has been demonstrated that there is significant emetogenic potential based on individual and cumulative AE data, prophylactic anti-emetics may be used using ASCO guidelines.

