	Hold VK-2019 and initiate antiemetic medication until resolves to Grade $\leq 2$ .
Grade ≥ 3 nausea/vomiting	If nausea and/or vomiting resolves to Grade $\leq 2$ within 21 days, VK-2019 may be restarted at the same dose (unless meeting criteria for a DLT) or a lower dose pending discussion between the investigator and Sponsor.
	If nausea and/or vomiting does not resolve to Grade $\leq 2$ after 21 days, permanently discontinue VK-2019 and observe the patient until the AE is resolved.
Grade $\geq$ 3 mean QTcF	Hold VK-2019 and perform regular ECGs (with repeat in 24 hours or less, then as clinically indicated) until resolution to Grade $\leq 1$ or baseline.
elongation	If QTc prolongation does not resolve to Grade $\leq 1$ or baseline within 21 days, permanently discontinue VK-2019.
Recurrence of the same Grade $\geq 3 \text{ AE}$	Hold VK-2019 and restart at one dose level lower if AE resolves to Grade $\leq 2$ within 21 days.
	If recurring AE does not resolve to Grade $\leq 2$ after 21 days, permanently discontinue VK-2019 and observe the patient until the AE is resolved.

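### Protocol Section 6.11 ends treatment after any DLT, but three rows of Section 9 bar only a same-dose restart and so leave open a lower-dose restart

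*Protocol*

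**What the plan says.** Section 6.11 (Patient Withdrawal) is mandatory. It opens with "Patients will be discontinued from treatment and begin long-term follow-up in the case of" and then gives a list that includes "DLT or unmanageable AE related to therapy". The bullet has no exception for dose reduction or Sponsor agreement.

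Section 6.9 (Duration of Therapy) makes that list the limit on treatment: "Patients may continue to receive treatment until meeting criteria for discontinuation/withdrawal, e.g., adverse events, disease progression, etc. as outlined in Section 6.11".

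Section 9 sets the rules for holding, reducing, resuming and stopping drug, up to "study drug discontinuance for AEs assessed to be at least possibly related to VK-2019". Three rows of its table mention DLTs: the general Grade 3 or higher row, Grade 3 or higher diarrhea, and Grade 3 or higher nausea/vomiting. Each says that, if the event falls to Grade 2 or lower within 21 days, "VK-2019 may be restarted at the same dose (unless meeting criteria for a DLT) or a lower dose", pending a discussion between investigator and Sponsor.

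Section 13 (Follow-up of AEs) lets the investigator re-challenge after selected AEs for which drug was stopped, and does not exclude DLTs.

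**The concern.** The same event can fall under both rules. A DLT must be at least possibly related to VK-2019 (Section 6.3), and Section 9 uses the same threshold. For such an event one section orders the drug stopped, while the other bars only one of two restart options.

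Two things depend on which section a site follows. The first is whether a patient is given the drug again after a dose-limiting event. The second is whether the event is counted as an AE leading to discontinuation. That count is part of the Phase 1 primary endpoint (Protocol 14.1.1), is summarized and listed under SAP 7.14.1, and is something the SRC weighs when it judges the RP2D (Section 6.6).

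**Working it through.** No sample size, error rate or other figure is involved, so the check is a comparison of texts.

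**1. What the parenthesis qualifies.** In all three rows the DLT exclusion stands directly after the same-dose option and before the lower-dose option. Read in order, a DLT removes the first option and leaves the second. If the intent were that a DLT ends treatment, the exclusion would be expected to govern the whole restart clause.

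**2. Whether a real event can meet both rules.** Take related Grade 3 diarrhea in Cycle 1, treated medically, that takes more than 3 days to return to Grade 1 or baseline but is at Grade 2 or lower within 21 days.

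| Provision | Result for this patient |
|---|---|
| Section 6.3.2, 3-day exemption | Not met, so the event is a DLT |
| Section 6.11 | Discontinue treatment |
| Section 9, diarrhea row | Condition for restart met; same dose barred; lower dose open after discussion with the Sponsor |

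The nausea/vomiting row works in the same way. The general row does so through the missed-dose criterion. The synopsis makes an AE that costs more than 7 days of dosing a DLT, while Section 9 allows restart up to day 21. A related Grade 3 or higher event with 8 to 21 missed days inside the DLT window is therefore a DLT for which Section 9 still offers a lower dose.

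**3. Whether other text settles it.**
- Section 6.9 points to Section 6.11 as the limit on treatment. That favours discontinuation, but the Section 9 wording stays in place, and no sentence says which section prevails.
- Section 6.10 gives a route back onto treatment after a confirmed CR. It is closed to patients who stopped for a treatment-related AE, so it neither supports nor explains a restart after a DLT.
- No row of the Section 9 table says that a DLT requires discontinuation.

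**4. What does not change.** The DLT is recorded when the event occurs, before any decision on restart. Under Section 6.2.1 a patient with at least one dose and a Cycle 1 DLT is evaluable whatever happens next. The DLT count, the escalation decision and the MTD are the same under either section.

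**5. A defect that affects the repair.** Section 6.3.2 prints the missed-dose criterion as fewer than 7 days, while the synopsis has more than 7. As printed, a related AE that cost one Cycle 1 dose would be a DLT. Any sentence that makes every DLT a permanent stop would carry that error into treatment decisions.

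**The case against.** The strongest case on the other side is that the two sections can be reconciled. Section 6.11 is mandatory, the restart rows are permissive and need Sponsor discussion, and a site that always discontinues after a DLT breaches neither. The rows also cover related Grade 3 or higher events in every cycle. Most of those cycles lie outside the 28-day DLT window, so the lower-dose option has a full meaning for events that are not DLTs. Section 6.10 is consistent with Section 6.11 being in control.

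Much of this stands. It shows that a cautious reader reaches the right answer. It does not show that the text leads every site there, because a site that applies the three rows as written, with the Sponsor's agreement, could re-dose a DLT patient in breach of Section 6.11.

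A reader might go further and infer that the whole Section 9 table contradicts Section 6.11. The documents do not support that:
- The QTcF row gives no restart dose.
- The Grade 2 row says "Continue VK-2019 at the same dose level". An AE managed that way would not normally cost doses, so the missed-dose route to a DLT largely excludes itself. What remains is an event that the SRC declares a DLT, which the SRC is already reviewing.
- The recurrence row tells sites to "Hold VK-2019 and restart at one dose level lower if AE resolves to Grade" 2 or lower, but it will mostly concern events that were not DLTs.

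**Conclusion.** The conflict is real and narrow: Section 6.11 against three rows of Section 9, on restart at a lower dose after a DLT. It should be fixed because it governs re-exposure after a dose-limiting event and the repair is small. The effect on reporting is limited to a descriptive count, since Protocol Section 14 plans no confirmatory inference.

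The number of patients affected is unknown and may be zero. A reader might try to size it by applying the Phase 1 hypothesis (DLTs in less than 18% of patients) to planned enrollment. That is not supported. The 18% is a ceiling in a hypothesis. A cohort closes once two patients have a DLT, which holds the number of DLT patients down. The result would also count patients with a DLT, whereas the problem concerns only those re-dosed afterwards, and the documents give no figure for that share.

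The conclusion assumes that the parenthesis is read where it stands. The SRC Charter was not available for this review. The SAP is written for an abbreviated CSR and reports that no biopsies were collected. This suggests that enrollment may have ended but does not prove it, because biopsies were optional and confined to Phase 2a.

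**What to change.** 1. Correct the missed-dose criterion in Section 6.3.2 to more than 7 days, to match the synopsis. This has to come first, for the reason in step 5 of the working.
2. In each of the three Section 9 rows, replace the parenthesis with a leading condition: *Unless the event is a DLT, in which case VK-2019 is permanently discontinued per Section 6.11, VK-2019 may be restarted at the same or a lower dose*, followed by the existing discussion requirement. Simply deleting the parentheses would be worse, because they are the only mention of DLTs in those rows.
3. Exclude DLTs from the re-challenge sentence in Section 13 (Follow-up of AEs).

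If restart at a reduced dose after a DLT is what the Sponsor intends, keep the correction in step 1. In place of steps 2 and 3, add to the Section 6.11 DLT bullet: *except where restart at a lower dose is agreed with the Sponsor under Section 9*.

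If dosing has ended, add the action taken and any restart dose to the first-cycle DLT listing already planned in SAP 7.14.1.

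The cost is one corrected symbol, three reworded sentences and one clause. The alternative needs the corrected symbol and one clause. After dosing, it is two columns in a planned listing, most of which can already be obtained by matching the discontinuation and exposure listings.

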## 7 STUDY DRUG: VK-2019

#### Description, Supply and Storage of Investigational Drugs

7.1.1 Classification

VK-2019 is an anti-viral compound being tested for its effect on cancer.

7.1.2 Mechanism of Action

VK-2019 binds to EBNA1 and inhibits EBNA1 DNA binding activity.

7.1.3 Metabolism

Two VK-2019 metabolites were observed when incubated with liver microsomes: A hydroxylated form and a glucouronidation form. These forms are likely the major routes of clearance of VK-2019.

7.1.4 Drug interactions

Drug interaction studies with VK-2019 have not been conducted. The following information is based on results from *in vitro* studies with VK-2019. All concomitant medications must be recorded and approved by the sponsor at study entry and up to the end of Cycle 2.

VK-2019 did not inhibit CYP450 1A2, 2D6 or 3A4 in vitro.  $IC_{50}$  values were greater than 50  $\mu$ M,

the highest concentration that was tested. In addition, VK-2019 did not induce the mRNA expression of drug-metabolizing CYP450 1A2, 2B6 and 3A4 in primary human hepatocytes from 3 different donors. Therefore, the interaction of VK-2019 with metabolism of drugs through these P450 subtypes appears unlikely at clinical concentrations. In cell assay, VK-2019 was classified as a substrate of OATP1B3 transporter at low concentration, but not at high concentrations. The influx rate of atorvastatin was increased in the presence of VK-2019, suggesting that OATP1B3 mRNA expression was induced. It is not known how the administration of VK-2019 will affect the absorption of drugs that are transported by OATP1B3, for example, atorvastatin. See Appendix 2 for details regarding disallowed medications.

7.1.5 VK-2019 capsules

VK-2019 will be provided in capsules containing either 30 mg or 200 mg VK-2019.

7.1.6 Storage and handling

VK-2019 is formulated in capsules, in 30 mg and 200 mg per capsule formulations. The capsules are packaged in High-Density Polyethylene (HDPE) bottles, with protection from moisture and should be handled with care.

The site Investigator must ensure that all investigational drug supplies are stored in a locked, safe area at room temperature (15-25°C) with access limited to authorized study staff. Investigational drug supplies should not be repackaged in any way.

Once patients are given study treatment, they will be asked to store them away from moisture at room temperature.

7.1.7 Side Effects

Information on pre-clinical toxicity and updated adverse event information if available are presented in the Investigational Drug Brochure.

# 8 TREATMENT PLAN

## Patient Enrollment and Allocation to Treatment

Each patient will provide informed consent prior to any study related assessments. In some cases, procedures performed as standard of care prior to signing consent may be allowed as assessments of a patient's eligibility, e.g., scans performed on a patient's prior treatment regimen serving as baseline scans for this study so long as they will be within the 28-day screening window.

Upon determination that the patient meets all eligibility criteria, the Investigator or designee will enroll the patient according to the procedures described by the Sponsor. Each enrolled patient will be assigned a unique subject number by the Sponsor or its designee.

Recruitment into the study will be conducted in a controlled manner. No patient will be enrolled without prior authorization from the Sponsor to ensure adherence with the study design. If a patient withdraws from the study, then the subject number cannot be reused, even in cases where the patient has withdrawn prior to receiving a dose of VK-2019. Dose level assignment will be controlled by the Sponsor. The Investigator and/or designee will receive from the Sponsor confirmation of enrollment along with the assigned dose level. Sponsor will notify the other sites of slot allocation and will inform sites about the available slots, next possible enrollment dates after SRC review, etc.

Potential patients will NOT receive study drug until the entire enrollment process has been completed.

## **Dosage and Administration**

## 8.2.1 Availability

Upon activation, study centers will receive a supply of VK-2019. Re-supplies of VK-2019 will be made at regular intervals during the course of the study based upon need. The Sponsor should be contacted for any issues related to drug supplies.

## 8.2.2 Preparation and Dispensing

VK-2019 will be provided in HDPE bottles containing either 30 mg or 200 mg capsules with protection from moisture. Patients should be given sufficient supply to last until their next study visit or for an entire cycle, depending upon institutional policy and study team discretion.

VK-2019 must be handled and administered with care. Patients should be instructed to keep their medication bottles provided at room temperature in a dry and safe place and not transfer it to any other containers.

# 8.2.3 Administration and Accountability

Site personnel must ensure that patients clearly understand the directions for self-medication. Patients should record daily administration of each study drug in their patient diaries. If a patient misses a dose, they must be instructed not to "make it up" or double the dose on the next day. Patient diaries and pill counts by research staff at least once each cycle will be used to determine actual dosing.

If a patient vomits any time after taking a dose, they must be instructed not to "make it up," but to resume subsequent doses the next day as prescribed.

On PK days (Tables 4-6), VK-2019 will be administered during the clinic visit to optimally control for PK times relative to dosing. On all other days, patients will be instructed to self-administer VK-2019 in the morning on an empty stomach with a glass of water at approximately the same time each day. Patients must fast for one hour before and two hours after each dose.

Patients will be instructed to swallow VK-2019 capsules whole and not to chew them prior to swallowing. No capsule should be ingested if it is broken, cracked, or otherwise not intact. When a patient is required to ingest more than six capsules per daily dose and the patient reports difficulties doing so, it is allowable to take the dose in split doses during the morning hours.

Medication errors are reportable irrespective of the presence of an associated AE/SAE, including:

- Medication errors involving patient exposure to the product,
- Potential medication errors or uses outside of what is foreseen in the protocol that do or do not involve the participating subject.

Whether or not the medication error is accompanied by an AE, as determined by the investigator, the medication error and, if applicable, any associated AEs are to be captured on an AE CRF page.

# 9 PATIENT MONITORING, TOXICITY MANAGEMENT, AND DOSE MODIFICATIONS

Each patient will be assessed for the development of any toxicity as outlined in Section 13. Dose adjustments will be made according to the system showing the greatest degree of toxicity. The table below outlines parameters for dose holds, dose reductions, resuming dosing, and study drug discontinuance for AEs assessed to be at least possibly related to VK-2019.

Adverse Event	Action with VK-2019 and Toxicity Management
All Grade 1 AEs	Continue VK-2019 at the same dose level. Manage with supportive therapy at the Investigator's judgment.
All Grade 2 AEs	Continue VK-2019 at the same dose level. Manage with supportive therapy at the Investigator's judgment.
All Grade $\geq$ 3 AEs (unless otherwise noted below)	Hold VK-2019 and administer supportive therapy as required in accordance with local practice/guidelines.
	If AE resolves to Grade $\leq 2$ within 21 days, VK-2019 may be restarted at the same dose (unless meeting criteria for a DLT) or a lower dose pending discussion between the investigator and Sponsor.
	If AE does not resolve to Grade $\leq 2$ after 21 days, permanently discontinue VK-2019 and observe the patient until the AE is resolved.
Grade ≥ 2 diarrhea	Manage with Loperamide (4mg at first onset, followed by 2mg every 2-4 hours (or with each loose bowel movement) until diarrhea free for 12 hours (maximum daily dose: 16 mg/24 hours). If loperamide is ineffective, consider adding Lomotil (5 mg, four times a day), or tincture of opium (15- 20 drops orally every 4 hours), or octreotide (150 to 300 mcg SQ twice daily). Modifications to this regimen can be made per local standard practice.
	Hold VK-2019 and manage as above until resolves to Grade $\leq 2$ .
Grade $\geq$ 3 diarrhea	If diarrhea resolves to Grade $\leq 2$ within 21 days, VK-2019 may be restarted at the same dose (unless meeting criteria for a DLT) or a lower dose pending discussion between the investigator and Sponsor.
	If diarrhea does not resolve to Grade $\leq 2$ after 21 days, permanently discontinue VK-2019 and observe the patient until the AE is resolved.

Adverse Event	Action with VK-2019 and Toxicity Management
Nausea/vomiting, all grades	Standard antiemetics for the treatment of nausea and/or vomiting may be used. If it has been demonstrated that there is significant emetogenic potential based on individual and cumulative AE data, prophylactic anti-emetics may be used using ASCO guidelines.
	Hold VK-2019 and initiate antiemetic medication until resolves to Grade $\leq 2$ .
Grade ≥ 3 nausea/vomiting	If nausea and/or vomiting resolves to Grade $\leq 2$ within 21 days, VK-2019 may be restarted at the same dose (unless meeting criteria for a DLT) or a lower dose pending discussion between the investigator and Sponsor.
	If nausea and/or vomiting does not resolve to Grade $\leq 2$ after 21 days, permanently discontinue VK-2019 and observe the patient until the AE is resolved.
Grade $\geq$ 3 mean QTcF	Hold VK-2019 and perform regular ECGs (with repeat in 24 hours or less, then as clinically indicated) until resolution to Grade $\leq 1$ or baseline.
elongation	If QTc prolongation does not resolve to Grade $\leq 1$ or baseline within 21 days, permanently discontinue VK-2019.
Recurrence of the same Grade $\geq 3 \text{ AE}$	Hold VK-2019 and restart at one dose level lower if AE resolves to Grade $\leq 2$ within 21 days.
	If recurring AE does not resolve to Grade $\leq 2$ after 21 days, permanently discontinue VK-2019 and observe the patient until the AE is resolved.

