## **Dose-limiting Toxicity**

DLTs will be determined based on the incidence and intensity of AEs assessed as being at least possibly related to VK-2019 and occurring up to 28 days after initiation of QD VK-2019 dosing on C1D0.

- 6.3.1 Dose-limiting Hematologic Toxicity
  - Grade 4 neutropenia > 7 days
  - Grade 4 thrombocytopenia or Grade 3 thrombocytopenia associated with bleeding or requiring platelet transfusion
  - Grade 3 febrile neutropenia
  - Grade 4 anemia or anemia that requires blood transfusion
- 6.3.2 Dose-limiting Non-hematologic Toxicities

- Any Grade 3 or higher non-hematology toxicity, excluding the following:
  - Toxicities assessed by Investigator as clearly related only to disease progression or intercurrent illness
  - Elevations of AST, ALT, and bilirubin, that correct to Grade 1 within one week and do not meet any of the definitions of acute liver injury as listed below
  - o Other asymptomatic laboratory abnormalities
  - Grade 3 fever without neutropenia that returns to Grade 1 or less within 3 days, and is not associated with hemodynamic compromise (including hypotension, or clinical or laboratory evidence of end organ perfusion impairment)
  - Grade 3 diarrhea, nausea, vomiting, or abdominal pain that returns to Grade 1 or baseline within 3 days and with medical intervention
  - Grade 3 pruritis or rash that returns to Grade 1 or baseline within 7 days or baseline with medical intervention
  - o Grade 3 fatigue
  - Grade 3 tumor flare (defined as pain, irritation or rash that localizes to sites of known or suspected tumor)

A DLT will also include:

- A laboratory finding of acute liver injury defined as:
  - Sustained (> 1 week) doubling of AST or ALT levels to no less than 4 x ULN, or sign of increasing functional liver impairment with > 2x baseline increase in total bilirubin
  - o Increased AST or ALT levels above 8xULN
  - Suspected acute liver injury (per Hy's law) ALT/AST > 3 x ULN in combination with Total Bilirubin > 2 x ULN in the absence of cholestatic injury (ALP < 2 x ULN) and no other cause identified.

- Any AE resulting in a patient missing < 7 days of dosing with VK-2019
- Any AE not otherwise meeting the criteria or timing of a DLT as defined above, but is declared a DLT by the SRC

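### For a recurrent Grade ≥ 3 QTcF prolongation still at Grade 2 and above baseline at day 21, one row of the Section 9 table stops VK-2019 for good and another restarts it one dose level lower

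*Protocol*

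**What the plan says.** The table in Protocol Section 9 covers events judged at least possibly related to VK-2019. Two of its rows apply to a repeat QTcF event.

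- **QTcF row.** For Grade ≥ 3 mean QTcF prolongation, VK-2019 is held and the site must "perform regular ECGs (with repeat in 24 hours or less, then as clinically indicated) until resolution to Grade $\leq 1$ or baseline". The stopping rule is "If QTc prolongation does not resolve to Grade $\leq 1$ or baseline within 21 days, permanently discontinue VK-2019". The trigger does not mention first or later episodes, and the row gives no restart dose.
- **Recurrence row.** For any repeat of the same Grade ≥ 3 event the instruction is "Hold VK-2019 and restart at one dose level lower if AE resolves to Grade $\leq 2$ within 21 days". Treatment ends only on a looser criterion: "If recurring AE does not resolve to Grade $\leq 2$ after 21 days, permanently discontinue VK-2019". QTcF is not excepted.

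Two other pieces of text could in principle settle priority. The general row is headed "All Grade $\geq$ 3 AEs (unless otherwise noted below", and the introduction to the table states "Dose adjustments will be made according to the system showing the greatest degree of toxicity".

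**The concern.** The sponsor set a stricter recovery threshold for QTcF than for any other event in the table. The recurrence row, read as written, relaxes that threshold for the patient who has already had the event twice. That patient could be re-dosed, at a lower level, without having met the protocol's own QTcF recovery criterion and at a point where the QTcF row requires treatment to end.

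Two sites could handle the same event in opposite ways, each following the table. What is at stake is patient safety and uniform conduct. ECG monitoring during the episode is not in question, because the QTcF row already requires it.

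**Working it through.** No sample size, power or error rate is involved, so the check sets the rows side by side and applies each to the same patient.

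**Step 1. Recovery thresholds in the Grade ≥ 3 rows of the Section 9 table**

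| Row | Recovery threshold |
|---|---|
| General Grade ≥ 3 | Grade ≤ 2 |
| Diarrhea | Grade ≤ 2 |
| Nausea/vomiting | Grade ≤ 2 |
| QTcF | Grade ≤ 1 or baseline |
| Recurrence | Grade ≤ 2 |

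Four of the five use Grade ≤ 2. Only QTcF differs, so it is the only event for which the recurrence row can clash with an event-specific row.

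**Step 2. Both rows applied to a recurrent, related Grade ≥ 3 QTcF event, by status at day 21**

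| Status at day 21 | QTcF row | Recurrence row | Agree? |
|---|---|---|---|
| Grade ≤ 1 or baseline | No discontinuation | Restart one level lower | Yes |
| Grade 2, above baseline | Permanent discontinuation | Restart one level lower | **No** |
| Grade ≥ 3, above baseline | Permanent discontinuation | Permanent discontinuation | Yes |

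One of the three day-21 states conflicts. These are logical cases and carry no probabilities.

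**Step 3. Before day 21.** Both rows say within 21 days, so the restart thresholds also differ earlier. Take a patient who reaches Grade 2 on day 5 and Grade 1 on day 15 (illustrative days). The recurrence row permits a restart from day 5, while the QTcF row keeps the drug on hold until day 15, a difference of 15 − 5 = 10 days. This patient is in the agreeing first state at day 21, so the day-21 table understates the mismatch.

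**Step 4. Search for a priority rule**

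- The carve-out in the general row's heading qualifies that row only. It does not rank the QTcF row against the recurrence row, and both lie below it.
- The sentence on the greatest degree of toxicity chooses between systems. Here there is one system and one event.
- The SAP contains no dose-modification rules.

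**Step 5. Can the case arise?** The QTcF row ends treatment only for unresolved events, so a patient who recovers can resume and have a second event. A related Grade ≥ 3 first event in Cycle 1 would generally be a DLT under Section 6.3.2 ("Any Grade 3 or higher non-hematology toxicity, excluding the following"), and Patient Withdrawal lists "DLT or unmanageable AE related to therapy" as a reason to end treatment. The DLT window is 28 days from C1D0, however, and treatment is open-ended, so later events are not normally DLTs.

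**Step 6. Size.** The documents give no QTcF event rate. Assuming 0 to 1 patient meets the case, with about 68 planned (Sample Size Determination), the range is 0/68 = 0% to 1/68 = 1.5%. The upper limit of one patient is an assumption.

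**The case against.** The strongest reply is that the rows can be read together: the QTcF row decides whether treatment ends, and the recurrence row sets the dose for any restart that is still allowed. Permanent discontinuation leaves nothing to restart, and a sensible investigator would follow the row that names QTcF. That reading is reasonable, but it is inference. The QTcF row is specific to the event and the recurrence row is specific to the episode. Because the QTcF row gives no restart dose, an investigator managing a repeat event is led to the recurrence row and its Grade ≤ 2 threshold.

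The second reply is rarity, and it stands:

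- While dosing continues, ECGs are scheduled only at C1D0, C1D14 and C2D0 in Phase 1, and at C1D0 and C2D0 in Phase 2a. Apart from the C2D0 visit window, a first event on a scheduled ECG falls within the DLT period. A later recurrence would mostly need an unscheduled ECG to be seen.
- Background reports no hERG binding up to 50 µM.
- Exclusion criterion 12 bars a mean screening QTcF above 470 ms.
- The investigator or sponsor can withdraw any patient for safety.

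These points limit how often the conflict would matter. They do not remove it.

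The SAP was also written for an abbreviated CSR, plots EBV DNA for Phase 1 Dose Escalation only and states that no biopsies were collected. The trial may therefore have treated fewer than 68 patients, and an amendment may come too late to matter here.

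**Conclusion.** The inconsistency is real on the text and minor. For a recurrent related Grade ≥ 3 QTcF event at Grade 2 and above baseline on day 21, the table directs both permanent discontinuation and a restart, with no rule for choosing. The restart criteria also differ earlier in the hold.

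The reach is narrow: one event type, and a patient who has that event twice. The 0% to 1.5% range is only an indication, since it rests on the assumed 0 to 1 patient and on planned enrollment. No endpoint, error rate or sample size changes. Confidence in the textual conflict is high, because it depends only on the two rows and the absence of a ranking rule.

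**What to change.** In the recurrence row, add a parenthesis after the Grade ≤ 2 restart threshold: (for QTcF prolongation, Grade ≤ 1 or baseline). Then tie that row's stopping sentence to the same threshold, so that a repeat event not reaching it by 21 days ends treatment.

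Re-running the three day-21 states with this wording gives restart one level lower, discontinue and discontinue. All agree with the QTcF row, so conflicts fall from 1 of 3 to 0 of 3. The difference before day 21 also disappears, and every other event is handled as now.

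The cost is a few words at the next protocol amendment, with no added visits, ECGs or patients. The drawback is that an occasional patient at Grade 2 and above baseline at day 21 of a repeat episode will come off treatment instead of continuing at a lower dose. If dosing in this trial has ended, carry the correction into any later protocol that reuses the table. Patient Withdrawal does allow some patients to continue VK-2019 after study termination, so the wording could still matter for them.
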